
Justification

We wish to demonstrate that the use of with autologous MSCs is effective as a treatment option for knee OA grades, II and III. In a large number of cases it is possible to improve the pain, function and quality of life of patients without the side effects of conventional treatments. In other cases, avoid progression to more severe stages that require joint replacement surgery. This research aims at contributing with a low-cost regenerative technique in order to change the course of the disease and significantly reduce public and private sector expenses generated by conservative and surgical OA treatments.

Main goals

- a. The aim of the present study will be to compare three types of intra-articular injections of MSC populations obtained from two clinically relevant sources: injections containing BM-MSC or AD-MSC or a combination of both of them BM-MSC and AD-MSC, in a randomized non blind clinical trial.
- b. To assess the efficacy and safety of treatment with containing BM-MSC or AD-MSC or a combination of both of them BM-MSC and AD-MSC, in relation to pain, function and quality of life in patients with knee OA.

Hypothesis Testing

H1: The combined use of BM-MSC and AD-MSC is superior for pain management in knee OA, than the use of BMSC or AD-MSC alone.

H0: The combined use of MSC from bone marrow and adipose tissue is not superior to the use of MSC derived solely from bone marrow or solely from adipose tissue in the treatment of pain and function in patients with knee OA.

MATERIALS AND METHODS

1. Study design

The present study will be conducted from June 2020 to December 2021 at the Omnihospital, an affiliated center to the Universidad Católica de Santiago de Guayaquil Ecuador, and the support of the Instituto de Investigación e Innovación de Salud Integral, Medical Faculty of the same University and Maastricht University, The Netherlands. This will be a phase III trial, triple arm randomized open label dose to be conducted as a single intra-articular injection of MSC in 3 groups of patients with the diagnosis of knee OA grade II and III (Ahlbäck classification),²² one receiving BM-MSC other receiving AD-MSC and the other BM-MSC + AD-MSC.

2. Study population

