- viii. Place the "waste 60cc syringe" vertically on the Neogenesis 60 cc concentrating device. Using the BPS, push the PPP into the 60cc syringe until the buffy coat reaches 20ml outlined on the concentration device.
- ix. Remove the "60cc waste syringe". Place the "60cc Bone marrow collection" syringe on the concentrating device.
- x. Using the BPS push the remaining bone marrow until the syringe captures the buffy coat, a total volume of 10 - 20 cc. Cap the bone marrow collection syringe.
- xi. One ml of the total bone marrow will be sent for flow cytometry testing.
- xii. Subsequently, a single percutaneous intra-articular injection of the obtained MSCs will be done into the affected knee.

c. **AD-MSC PROCEDURE. GROUP 2.**

- i. Local anesthesia with Klein tumescent solution will be applied in the region of greater trochanter of hip and gluteus.
- ii. A 40 ml of pure fat will be extracted with two 60 ml syringe and 2.5 to 3 mm diameter cannula with equal luer lock spike. Physiological solution will be added and subsequently decanted in order to discard infranatant and remove traces of tumescence and blood (Repeat 2-3 times).
- iii. The obtained adipose tissue will be introduced into two 50 ml conical tubes. Reconstituted collagenase will be added with a 0.22 micron filter, 15 ml to each tube.
- iv. The tubes will be shaken for 20 minutes by placing them in the heater block or shaker. Then the two tubes will be centrifuged at 900 g for 5 minutes.
- v. Adipose tissue and saline supernatant will be carefully removed until the remaining pellet be approximately 5 ml. Using a pipette connected to the 20 ml syringe the pellet of stromal vascular factor will be extracted.
- vi. The obtained pellet will be transferred into two new sterile 50 ml tubes. Saline solution will be added until 45 ml be completed.
- vii. The cells of conical bottom of each of the tubes will be aspirated with a 20 ml syringe and pipette. A total volume of about 5 ml will be obtained.
- viii. In a new sterile 50 ml tube we will place a 100 µm cell strainer in order to gently transfer the cell suspension. Stromal vascular fraction (SVF) will be aspirated.
- ix. A 1 cc of the adipose tissue stem cell concentrate will be sent to the Molecular Biology Laboratory for quantification by flow cytometry in order to determine the volume and viability of obtained stem cells.

d. **BM-MSC + AD-MSC PROCEDURE. GROUP 3.**

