This study applies descriptive statistics for determining the frequency and proportions for demographic variables (age, gender, education, and ethnicity) and clinical states (severity of knee osteoarthritis, time with disease, comorbidities). Likewise, for calculating the mean and standard deviation of age, WOMAC scores (and each element of the scale) and VAS.

We utilize the two-way mixed ANOVA to compare the differences of means between treatment groups for each dependent variable (WOMAC scores, VAS, and radiological changes). With respect to the WOMAC scores, not only we will analyze the scores in general, but also each score value of the three different components separately (pain, stiffness, function). The tests will determine if there is an interaction between the dependent variable and the factors (independent variables). The factors will be the type of treatment (between subjects) and time (within subjects). For the type of treatment, it

is categorized into: BMSCS only, AD-MSc only, and BM-MSc and AD-MSc combined.

As for the time factor, this will differ according to the dependent variable held for analysis. For example, the analysis of WOMAC and EAV scores will be evaluated in 6 different periods of time. The patients will be asked to respond to our questionnaires three weeks before the intervention and 1, 3, 6, 9, and 12 months after intervention (surgery). With respect to radiological changes, the T2 mapping MRI will be performed twice before the procedure and again six months later.

To guarantee the reliability of the analysis, we will test the atypical values by utilizing box diagrams and the normality with the method of Shapiro-Wilk. Furthermore, the homogeneity of variations will be evaluated with inferential statistic Levene tests, while the homogeneity of covariances with multivariate statistical Box's M test. Consequently, to comply with the hypothesis sphericity, a Mauchly's test will be conducted. In the case of a violation of an assumption, different tests will be utilized.

Finally, in the case of a treatment complication, there will be mixed lineal models generalized for determining the probability of each intervention. The complications considered in this investigation are pain and hematomas in the surgical place where stem cells were extracted, knee pain, and synovial effusion.

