Data will be analyzed using SPSS software version 24.0. for every test, a *p-value* lower than 0.05 will be considered as the statistical significance level.

SAFETY

Absence of immunological reaction and disease transmission due to the fact that MSCs belong to the same patient. Wakitani²⁷ from the University of Osaka Japan demonstrated in an 11-year follow-up study that MSC did not induce tumor growth or infection in any patient treated for cartilage lesions.

Chris and colleagues²⁸ reported no adverse events after using intra-articular injection of 1.0×10^8 AD MSCs in patients with knee OA, and showing improvement of joint function.

Peeters et al²⁹. evaluated 8 studies that involved 844 MSC-treated patients with intra-articular injected culture expansion. They concluded that there are no opposing arguments for the intra-articular application of MSC.

Systematic reviews have all been in favor of the safety in intra-articular - injections of MSCs. However, great caution is warranted with culturing and expansion of MSCs³⁰.

DISCUSSION

The function of MSCs has been explored under the influence of bioactive carriers such as platelet-rich plasma (PRP). Platelets contain greater than 1500 protein based factors

with bioactive ability³¹. This broad spectrum of compounds includes growth factors, peptide hormones, chemokines, fibrin and also proteins with anti-bacterial and fungicidal properties.

Growth factors released by platelets may potentially play a positive role in the up regulation of MSCs. TGFβ1 is seen to reduce collagen type I gene expression and up regulate expression of collagen type II and aggrecan genes³². Further, TGFβ1 works in association with basic Fibroblast Growth Factor (FGF2) to assist in the migration of stromal cells to a site of injury^{30,33}.

The combination of PRP with MSCs in intra-articular injections has shown increased collagen type II expression and reduced chondrocyte apoptosis³⁴.

Most recently, Phase I and II trials using expanded adipose derived MSCs in the treatment of OA have shown MRI evidence of cartilage regrowth³¹. Following a single intra-articular injection of 100 million MSCs, radiological (MRI) follow-up at 6 months showed increased cartilage volume³⁰.

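### The planned safety analysis covers four local complications only; infection and reactions to collagenase, anaesthetic, sedation or procaine have no planned definition, tabulation or comparison by arm

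*Combined protocol and SAP*

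**What the plan says.** Main goal (b) is "To assess the efficacy and safety of treatment" in relation to pain, function and quality of life.

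The Statistical Analysis section gives one safety analysis: "in the case of a treatment complication, there will be mixed lineal models generalized for determining the probability of each intervention". It then fixes the scope: "The complications considered in this investigation are pain and hematomas in the surgical place where stem cells were extracted, knee pain, and synovial effusion". There is no category for other events, infection, systemic reaction or serious events.

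The Safety section opens with "Absence of immunological reaction and disease transmission due to the fact that MSCs belong to the same patient". It deals with infection by citing an earlier follow-up study in which "MSC did not induce tumor growth or infection in any patient treated for cartilage lesions".

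The study flow chart (section 7, Follow up) has an adverse event evaluation row. As extracted, its five marks align with Visits 5 to 9 (Week 6 to Month 12). Nothing in the document defines what is recorded there, how it is graded, what counts as serious, or how it is analysed.

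The procedures expose patients to agents other than their own cells:

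- Section 4.a.vii gives every patient two procaine injections, at Weeks 1 and 3.
- Section 6.a has the harvest done under local anaesthesia and sedation.
- Section 6.c, for the adipose product, adds: "Local anesthesia with Klein tumescent solution will be applied in the region of greater trochanter of hip and gluteus", and "Reconstituted collagenase will be added with a 0.22 micron filter, 15 ml to each tube".

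**The concern.** The list is worded as the full set of complications under study, and all four items are local. Followed literally, it leaves joint infection, harvest-site infection and any reaction to a reagent or anaesthetic outside the only planned safety analysis. The plan raises infection and immune reaction itself, but settles them by argument or citation instead of making them outcomes.

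The argument from autologous cells is about the cells. It says nothing about collagenase, tumescent solution, sedation or procaine.

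Two features make this matter for a three-arm comparison. First, collagenase and tumescent solution come with the adipose product, so reactions to them could fall unevenly across arms. Second, knee pain and effusion are listed with no separate place for infection. Every patient enters with chronic knee pain and a VAS of at least 4, so an infected joint could be absorbed into a listed item. With so few patients, one such event is informative only if it can be identified.

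**Working it through.** **1. The plan's own figure.** The only sample-size calculation is for the efficacy interaction. Inputs from the Statistical Analysis section: f = 0.25, 3 groups, 3 repetitions, correlation 0.5, epsilon 1, alpha 0.05, target power 0.95.

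- λ = f² × N × m / (1 − ρ) = 0.0625 × 54 × 3 / 0.5 = 20.25, as stated.
- df = (3 − 1)(3 − 1) = 4 and (54 − 3)(3 − 1) = 102. Power is 0.958; N = 51 gives 0.946.

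So 54 (18 per arm) reproduces. No safety quantity enters it.

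**2. Exposure set against the planned analysis.**

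| Exposure or harm | Group 1 | Group 2 | Group 3 | On the list of four? |
|---|---|---|---|---|
| Procaine reaction | yes | yes | yes | no |
| Anaesthetic or sedation reaction | yes | yes | yes | no |
| Tumescent solution reaction | no | yes | yes* | no |
| Collagenase reaction | no | yes | yes* | no |
| Joint or harvest-site infection | possible | possible | possible | no |
| Harvest-site pain, haematoma | yes | yes | yes (two sites) | yes |

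*Section 6.d says only that the two products are joined in one syringe. It is assumed that the adipose part is prepared as in section 6.c. On that assumption (18 + 18) / 54 = 36/54 = 67% receive collagenase-processed product.

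**3. Timing.** Preparation is marked at Visits 1 and 3 (Weeks 1 and 3). Adverse event evaluation is first marked at Visit 5 (Week 6). A reaction at either procaine visit has no scheduled evaluation.

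**4. What a wider list could deliver.** The documents give no rates for these harms in this product, so the rates below are assumptions. Chance of at least one event = 1 − (1 − p)^n:

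| Assumed p | n = 18 | n = 36 | n = 54 |
|---|---|---|---|
| 0.1% | 1.8% | 3.5% | 5.3% |
| 1% | 17% | 30% | 42% |
| 2% | 30% | 52% | 66% |
| 5% | 60% | 84% | 94% |

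With zero events, the one-sided 95% upper limit is 1 − 0.05^(1/n): 15.3% for n = 18, 8.0% for n = 36, 5.4% for n = 54.

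Two-sided Fisher test at 0.05, 18 v 18: 4 v 0 events gives p = 0.104 and 5 v 0 gives p = 0.046, so at least 5 v 0 is needed. Power against a 0% comparator is 0.15% at a true rate of 5%, 2.8% at 10% and 28% at 20%. For 36 v 18, at least 8 v 0 is needed (p = 0.042).

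**The case against.** The strongest reply is the flow chart. Its adverse event row is not restricted to the four complications, so a septic knee or a reaction after the procedure could be recorded and described. This stands. A reader might infer that the trial cannot show serious harms, or that such events would go uncounted; the documents do not support that. The row does not close the gap, however, because it is undefined, unlinked to the analysis, and starts after the procaine visits.

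Other stronger readings also fail:

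- That an infected joint will be coded as knee pain or effusion. There is no coding rule; it could happen, no more.
- That the chance of an infection among 54 patients (5% to 42% at assumed rates of 0.1% to 1%) measures the damage done by the list. It measures whether an event occurs, not what the list changes.
- That the list hides a difference between arms which the trial would otherwise detect. At 18 per arm, no list supports a test for rare harms.
- That all the omitted harms differ by arm. Procaine, local anaesthesia, sedation, a harvest and a joint injection are common to all groups. Group 3's second harvest site is partly covered by the listed harvest-site items.
- That the adipose processing is careless. Section 6.c specifies sterile tubes and filtered collagenase.

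It can also be said that the Safety section is background and its autologous argument makes no claim about collagenase. That is fair, but it is also the only place where immune reaction is considered.

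**Conclusion.** The point holds as a gap in definition and reporting. Safety is a main goal, yet infection and reactions to non-cell agents have no planned definition, no table and no comparison by arm. The adverse event row allows recording but specifies nothing further. The gap bears on the comparison because two of the unlisted exposures, collagenase and tumescent solution, are confined to the adipose product.

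The 36-of-54 count rests on Group 3's adipose product being prepared as in Group 2. The timing point rests on the flow chart columns as extracted. The size of any missed harm cannot be stated, since no event rates are given. Correcting the plan makes each event identifiable and reportable; it does not create a usable between-arm test. The sponsor should make the change.

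**What to change.** **Statistical Analysis.** Replace the closed list with all adverse and serious adverse events from the flow chart row. Define them and tabulate patients with at least one event by arm, with exact confidence intervals. Keep the four listed items and name in addition:

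- joint infection and harvest-site infection, each coded separately from knee pain and effusion;
- hypersensitivity or systemic reaction (collagenase, tumescent or other anaesthetic, sedation, procaine);
- any event needing hospital admission or knee re-intervention.

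State that 18 per arm does not support tests for rare harms, and give the upper limit for zero events so that an empty cell is not read as evidence of safety.

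**Flow chart.** Refer the adverse event row to these definitions and start recording at the first procaine visit. As extracted, the chart marks informed consent at Visit 2, after the first preparation visit; those two marks need to be reconciled.

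**Safety section.** Present immunological reaction as an outcome to be assessed, not as absent because the cells are autologous.

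**Cost.** A longer form, a few more table rows, and a less favourable safety statement. Treatment and sample size are unchanged.
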